6.5.1 Primary Efficacy Endpoint

The primary efficacy objective is to evaluate the clinical effect of prophylactic emicizumab compared with no prophylaxis on the number of bleeds over time. The definition of a bleed is described in Section 4.5.8. The primary endpoint is based on treated bleeds.

The primary efficacy analysis will be conducted after all randomized patients (and a minimum of 40 patients previously treated with prophylactic FVIII) have completed

24 weeks in the study or the last randomized patient yet to complete 24 weeks in the study discontinues study participation, whichever occurs first, and using an intent-to-treat principle. The comparison of the number of bleeds over time between the randomized treatment arms will be performed using an NB regression model, which accounts for different follow-up times, with the patient's number of bleeds as a function of randomization and the time that each patient stays in the study included as an offset in the model. The model also includes the number of bleeds (< 9 or ≥ 9) in the last 24 weeks prior to study entry as a stratification factor in the randomization. This analytic model estimates the rate ratio, λ_t/λ_c , which quantifies the risk of bleeding associated with prophylactic emicizumab (λ_t) in comparison to no prophylaxis (λ_c). Statistical significance is controlled at the 2-sided, 0.05 alpha (α) level. Of note, hierarchical testing is used to account for multiple testing and the first test to be included in the hierarchy is the emicizumab 1.5 mg/kg/wk maintenance dose versus control. The second test will be 3 mg/kg/2wks maintenance dose versus control. The description below covers both hypotheses to be tested:

H_0 (null hypothesis): Rate Ratio = 1 versus H_1 (alternative hypothesis): Rate Ratio $\neq 1$.

The treatment effect therein is based on a contrast statement in the model with use of the SAS GENMOD procedure. Statistical significance at the prespecified alpha level will be based on a Wald testing procedure. Bleed rates for prophylactic emicizumab and no prophylaxis and the rate ratio will be presented and include 95% confidence intervals.

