## **2.4 DETERMINATION OF SAMPLE SIZE**

The sample size for this study is based on clinical rather than statistical considerations, taking into account the limited number of patients with hemophilia A without inhibitors available for participation in clinical studies and in an effort to collect sufficient data to assess the safety and efficacy of emicizumab.

The sample size calculation is based on the evaluation of the primary efficacy endpoint, defined as the number of bleeds over time (i.e., bleed rate) with emicizumab (treatment group,  $\lambda_t$ ) versus no prophylaxis (control group,  $\lambda_c$ ), which are said to follow a negative binomial (NB) distribution. With consideration of enrollment feasibility, a sample size of 75 patients, assuming an allocation ratio of 2:2:1 (30 patients in each randomized treatment group and 15 patients in control group), will achieve a power of more than 90% assuming a mean ABR of 4 and 14 bleeds (with variances = mean  $\times$  10) for the emicizumab treatment and control arms respectively, representing an expected 71% reduction in the ABR compared to the control arm. Initial sample size calculations were performed with East®, Version 6 (Cytel, Cambridge, MA), assuming the patients from each treatment group are followed up to 0.5 units of time (i.e., 24 weeks).

However, the above approach to sample size calculation assumes similar follow-up for each patient. Because this is unlikely to be seen in the study, power was also estimated by simulation to account for different follow-up times among patients. Conducting simulations on the basis of an NB regression model including an offset variable to account for variable follow-up times, with all other assumptions remaining the same as previously described, the sample size is projected to have greater than 90% power at the 2-sided 0.05 level of significance.

The analysis will include all enrolled patients regardless of their length of follow-up. Therefore, to ensure the analysis is based on sufficient follow-up data and with 2:2:1 treatment to control randomization, approximately 34 patients in each randomized

[figure not shown]

emicizumab treatment arm (68 in total) and 17 patients in the control arm (approximately 85 patients in total) will be enrolled.

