With a minimum of 40 and a maximum of 60 patients enrolled in the open-label prophylactic emicizumab arm, and assuming a mean ABR of 4 and variance of  $4 \times 10$ , this number is considered sufficiently powered to evaluate the efficacy endpoint in this cohort; the treatment will be considered to provide adequate control if the upper limit of the one sided 97.5% CI around the mean ABR is less than or equal to 6.

The primary safety consideration in determining the sample size was the ability to sufficiently evaluate the safety profile of emicizumab as assessed by adverse events. Under the assumption that the occurrence of an adverse event can be adequately modeled using the binomial distribution, the planned sample size of 108–128 patients in the emicizumab treatment groups allows observation of adverse events having a true incidence rate of 1% with a probability of 0.66–0.72.

No sample size re-assessment of the initially specified sample size will be performed.

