#### **4.5.1 Primary Efficacy Endpoint**

The primary efficacy objective is to evaluate the clinical effect of prophylactic emicizumab compared with no prophylaxis on the number of bleeds over time. The definition of a bleed is described in Section [2.3.1](#). The primary endpoint is based on treated bleeds.

The comparison of the number of bleeds over time between the randomized treatment arms will be performed using an NB regression model, which accounts for different follow-up times, with the patient’s number of bleeds as a function of randomization and the time that each patient stays in the study (the length of the efficacy period) included as an offset in the model. The model also includes the number of bleeds ( $<9$  or  $\geq 9$  according to the eCRF data) in the last 24 weeks prior to study entry as a stratification factor. This analytic model estimates the rate ratio,  $\lambda_t/\lambda_c$ , which quantifies the risk of bleeding associated with prophylactic emicizumab ( $\lambda_t$ ) in comparison to no prophylaxis ( $\lambda_c$ ). Statistical significance is controlled at the 2-sided, 0.05 alpha ( $\alpha$ ) level.

Of note, hierarchical testing is used to account for multiple testing and the first test to be included in the hierarchy is the emicizumab 1.5 mg/kg/wk maintenance dose versus

control. The second test will be 3 mg/kg/2wks maintenance dose versus control. A global approach using a model statement (within GENMOD) with a 3-level categorical effect for treatment (“1.5 mg/kg/wk,” “3 mg/kg/2wks,” or “no prophylaxis”) and an appropriate contrast statement will allow both tests to be performed via the following hypothesis

$H_0$  (null hypothesis): Rate Ratio = 1 versus  $H_1$  (alternative hypothesis): Rate Ratio  $\neq$  1.

Statistical significance at the prespecified  $\alpha$  level will be based on a Wald testing procedure. Bleed rates for prophylactic emicizumab and no prophylaxis and the rate ratio will be presented and include 95% CIs.

The number of bleeds can also be annualized for each patient using the following formula:

$$ABR = (\text{Number of bleeds} / \text{Total number of days during the efficacy period}) \times 365.25.$$

Both the model-based method (estimated ABR from the NB model) and the method using the above formula (calculated ABR) will be used to describe the study results.

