#### **4.5.2 Secondary Efficacy Endpoints**

Type I error for secondary endpoints is controlled through a hierarchical testing framework. The  $\alpha$  level is 0.05. Following the two statistical comparisons described in Section 4.5.1 for the primary endpoint (Arm A versus Arm  $C_{\text{control}}$  and Arm B versus Arm  $C_{\text{control}}$ ) the secondary endpoints are included in the hierarchy in the following order:

- A versus C randomized comparison: all bleeds
- B versus C randomized comparison: all bleeds
- A versus C randomized comparison: treated joint bleeds
- B versus C randomized comparison: treated joint bleeds
- A versus C randomized comparison: treated spontaneous bleeds
- B versus C randomized comparison: treated spontaneous bleeds
- D intra-patient: all bleeds
- D intra-patient: treated bleeds

- A versus C randomized comparison: Haem-A-QoL physical health at 24 weeks
- B versus C randomized comparison: Haem-A-QoL physical health at 24 weeks

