#### **4.5.2.4 Intra-Patient Comparison—Previous Prophylactic Patients**

[figure not shown]
The definition of treated bleeds and all bleeds for the intra-patient comparison (Section 4.1) is the same as described for the primary and secondary endpoints. The analysis methodology will be applied for Arm D (previous prophylactic patients) using the same NB regression model as for the primary endpoint with the exception that the SAS GENMOD procedure will include a REPEATED statement, to account for the intra-patient comparison. For intra-patient analysis of Arms A and B, see Section 4.5.2.6.

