#### **4.5.2.6 Secondary Efficacy Endpoints Not Included in the Hierarchy**

Treated target joint bleeds (defined according to Section 2.3.2.4) on emicizumab will be compared with no prophylaxis and will be analyzed using the same methodology as for the primary endpoint (i.e., using the NB regression model or the Van Elteren test).

[REDACTED]

The Haem-A-QoL total score, the EQ-5D-5L index utility score based on the U.K. value set, and the VAS at 24 weeks will be analyzed using the same analysis methodology as the Haem-A-QoL physical health subscore (i.e., via ANOVA).

The same analysis methodology for the intra-patient comparison within Arm D for treated bleeds and all bleeds will be applied for the pooled Arms A and B (episodic patients randomized to emicizumab). Of note: given the small number of NIS episodic patients that were randomized to either Arm A or B, it was considered that a pooled analysis was considered as more appropriate than two separate analyses.

Only a descriptive summary of the Haemo-QoL-SF will be provided because of the small number of adolescents randomized to the study.

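### The two alpha-controlled Arm D intra-patient tests have no small-sample safeguard; read as sandwich Wald tests, their two-sided size is about 6–8.5%, not 5%

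*SAP*

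**What the plan says.** - **Method.** SAP 4.5.2.4 analyses Arm D with the primary endpoint's negative binomial model. The only exception it states is that "the SAS GENMOD procedure will include a REPEATED statement, to account for the intra-patient comparison".
- **Test.** For that primary model, Protocol 6.5.1 says: "Statistical significance at the prespecified alpha level will be based on a Wald testing procedure". SAP 4.5.1 agrees that significance "will be based on a Wald testing procedure".
- **Error control.** SAP 4.5.2 says: "Type I error for secondary endpoints is controlled through a hierarchical testing framework", at 0.05. The entry "D intra-patient: all bleeds" is ninth of the twelve tests (two primary, ten secondary) and the treated-bleeds version is tenth. Both come before the two Haem-A-QoL tests.
- **Number of patients.** SAP 2.3.2.5 restricts intra-patient comparisons to NIS participants. SAP 2 requires at least 40 Arm D patients with at least 24 weeks in the NIS. SAP 2.4 sets the arm's size: "With a minimum of 40 and a maximum of 60 patients enrolled in the open-label prophylactic emicizumab arm".
- **Pooled Arms A and B.** SAP 4.5.2.6 applies the same method outside the hierarchy, and pools the arms "given the small number of NIS episodic patients that were randomized to either Arm A or B". It gives no count.

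Neither document names a working correlation, a covariance estimator, a small-sample correction or an alternative test for these analyses.

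**The concern.** With a REPEATED statement each patient is one cluster contributing two periods. If inference uses the empirical (sandwich) variance and a normal reference, it relies on having many clusters. With 40–60 clusters and skewed, overdispersed counts, the sandwich variance tends to be too small, and the normal cut-off of 1.96 makes no allowance for its imprecision. Both errors push towards rejection.

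These are the only tests in the hierarchy that set emicizumab against FVIII prophylaxis; every other test compares with no prophylaxis. Protocol 3.3 explains that a direct trial against FVIII prophylaxis was not feasible, so the within-patient result carries that comparison. A p-value just under 0.05, or an interval that narrowly excludes 1, would claim more than the method supports.

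**Working it through.** **1. Which dispersion is the plan's own?** SAP 2.4 assumes ABR 4 and 14, variance = 10 × mean, 30 versus 15 patients and 0.5 time units, and claims "greater than 90% power at the 2-sided 0.05 level of significance". With k = (variance − mean)/mean²:

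- Emicizumab: k = (40 − 4)/16 = 2.25. Control: k = (140 − 14)/196 = 0.643.
- Var(log rate ratio) = Σ[1/(λT) + k]/n = (0.5 + 2.25)/30 + (0.143 + 0.643)/15 = 0.0917 + 0.0524 = 0.144, so SE = 0.380.
- Power = Φ(ln 3.5/0.380 − 1.96) = Φ(1.34) = 91.0%.

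The stated power reproduces. If the variance is instead read per half-year, k = (20 − 2)/4 = 4.5 and (70 − 7)/49 = 1.286. Then SE = 0.512 and power is 69%. So k = 2.25 is the plan's value for ABR 4, and 4.5 serves as a heavier-dispersion case.

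**2. Simulated size for Arm D.** Inputs were ABR 4 in both periods (no effect) and 40–60 patients. Paired counts were Poisson with correlated gamma frailties of variance k. The following are assumptions, because the documents do not give them: within-patient frailty correlation from 0 to 1, NIS period 24 or 24–40 weeks, emicizumab period 24 or 24–52 weeks. The fit was a GEE-type negative binomial model with k by maximum likelihood, a log-time offset and an uncorrected sandwich SE, rejecting if |Z| > 1.96. There were 10,000 trials per scenario (Monte Carlo SE about 0.25–0.3 points).

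| NIS patients | k = 2.25 | k = 4.5 |
|---|---|---|
| 40 | 7.5–8.4% | 8.9–10.4% |
| 50 | 6.9–8.0% | 8.1–9.2% |
| 60 | 6.4–7.2% | 7.6–8.8% |

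Further runs at k = 2.25 with other frailty settings gave 7.1–7.6% at 40 patients, 6.9–7.1% at 48 and 5.8–6.9% at 60. A check with a packaged GEE routine (1,500 trials, Monte Carlo SE about 0.7 points) gave 6.9% at 40 and 7.2–7.3% at 60, almost the same under independence and exchangeable working correlation. In that check 3.3–3.7% of trials rejected in emicizumab's favour, against a nominal 2.5%. With lower dispersion (k = 0.64–1.0) size was about 5.6–7.2%.

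**3. Does the unstated choice matter?** In the same packaged check, the model-based SE gave 1.8–2.3% under independence and 6.3–6.5% under exchangeable correlation. Depending on options the SAP leaves open, size ran from about 2% to above 7%.

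**4. Alternatives on the simulated Arm D data.**

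| Method | k = 2.25 | k = 4.5 |
|---|---|---|
| Generalized score test (reject above 3.841) | 4.3–4.8% | 3.7–4.8% |
| Mancl-DeRouen-type sandwich, t on clusters − 1 | 5.4–6.7% | 6.7–8.8% |

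One further set of score-test runs fell as low as 3.0% at k = 4.5.

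**5. Pooled Arms A and B.** The patient number is not in the documents, so 10–30 is assumed, with 8–30 weeks in the NIS and 24–52 weeks on emicizumab. At the planning rate of 14 (k = 0.643), sandwich Wald size is 10.8–11.9% with 10 patients, 9.1–9.7% with 15, 7.7–8.3% with 20 and 6.5–7.0% with 30. The score test gives 3.4–4.9% over this range.

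**The case against.** The strongest reply is that the SAP never says an uncorrected sandwich Wald test will be used. The Wald sentence belongs to the primary endpoint; SAP 4.5.2.4 carries over the model and names neither a statistic nor a standard error. Depending on how the procedure is coded, the reported statistic could already be a score test. This stands in part: the sandwich Wald method is a reading, not a quotation. It is the natural reading, though, because REPEATED is the only stated exception to a model tested by Wald. If it is wrong, the plan still leaves open a choice that changes the size of a confirmatory test.

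Two further replies stand as limits. The inflation reaches the family-wise error only if all eight earlier tests reject. And the variance of 40 is a planning value for emicizumab; no variance is given for the NIS period on FVIII prophylaxis, so no single figure for the true size can be defended.

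A reader might infer an error of 10–15% for pooled Arms A and B. The documents do not support that. It needs roughly 10–20 patients, a number they do not give, and an ABR of 4 in both periods, although these patients entered with at least 5 bleeds in 24 weeks (ABR of at least 10). At the planning rate of 14, size exceeds 10% only near 10 patients. Nor does this analysis breach the controlled error rate, because it lies outside the hierarchy.

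**Conclusion.** The point holds for Arm D. Under the natural reading of SAP 4.5.2.4, with about 40–60 NIS patients and the plan's own ABR and variance, two-sided size is about 6–8.5%, which is 1.2 to 1.7 times nominal (6/5 and 8.5/5). Coverage of the 95% CI is correspondingly about 91.5–94%. With k = 4.5 size reaches about 10%. A reader might take 7.5–9% as the true error rate. At the plan's dispersion the runs reach 7.5% mainly towards 40 patients, and values near 9% need heavier dispersion.

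For pooled Arms A and B, the intervals are probably too short, by an amount the documents do not fix: size is about 6.5–12% if there are 10–30 patients at rate 14.

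All these figures rest on the Wald reading, gamma-mixed counts, and the assumed follow-up and within-patient correlation. The direction was the same in every Arm D sandwich Wald scenario. This should be corrected, but it is a moderate excess in a non-randomized before-and-after comparison late in the hierarchy, and it does not touch the primary analysis.

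**What to change.** In SAP 4.5.2.4:

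1. State that both Arm D p-values come from the GEE generalized score test, not the Wald/Z statistic.
2. Name the working correlation and the covariance estimator.
3. Obtain the 95% CI for the rate ratio by inverting the score test, so that interval and p-value agree. If a Wald interval is kept, use a bias-corrected sandwich with t on clusters minus 1, and say that it only partly restores coverage.

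Apply the same method to the pooled Arm A and B analysis in SAP 4.5.2.6.

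No new data or design change is needed. The cost is slightly wider intervals, slightly less power (the score test is mildly conservative here) and a little extra programming, mainly for the inverted interval.

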#### **4.5.2.5 Haem-A-QoL at 24 Weeks**

The physical health subscore of the Haem-A-QoL at 24 weeks will be analyzed using analysis of variance (ANOVA). The model will include the treatment group together with the baseline score and treatment by baseline interaction as covariates. As for the primary analysis, a global approach with a 3-level categorical effect for treatment (1.5 mg/kg/wk, 3 mg/kg/2wks, or no prophylaxis) will be produced for the comparisons of Arm A versus Arm C and Arm B versus Arm C.

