## **3. STUDY CONDUCT**

### **3.1 RANDOMIZATION ISSUES**

Patients who received episodic treatment with FVIII prior to study entry will be randomized in a 2:2:1 ratio to receive either emicizumab prophylaxis at 3 mg/kg/wk subcutaneously for 4 weeks, followed by 1.5 mg/kg/wk (Arm A) or 3 mg/kg/2wks (Arm B) subcutaneously, or to the control arm (no prophylaxis; Arm C). The time between screening and enrollment of eligible patients should be  $\leq 6$  weeks; otherwise, patients must be re-screened to determine if they continue to meet the inclusion and exclusion criteria. A central randomization procedure will be used for all patients who fulfill the

entry criteria at screening. A block based randomization method will be used, stratified by the number of bleeds in the last 24 weeks ( $<9$  or  $\geq 9$ ). The proposed randomization method is designed to balance treatment group assignment within the prognostic stratification factor.

Patients on FVIII prophylaxis prior to study entry will be enrolled in a separate therapeutic arm to receive emicizumab prophylaxis (Arm D).

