#### **4.5.3 Exploratory Efficacy Endpoints**

All bleeds will be characterized descriptively, including the type, location, and cause of bleed (surgery/procedure, traumatic, spontaneous). Bleed rates for spontaneous and traumatic bleeds will be calculated.

For EQ-5D-5L, Haem-A-QoL, and Haemo-QoL-SF, exploratory analyses include descriptive analyses of change from baseline and between group comparisons over time for each individual subscale and the overall score. In addition, a paired t-test will be conducted to compare the 24-week with the baseline score for the EQ-5D-5L and Haem-A-QoL questionnaires by treatment arm separately. Due to the limited number of adolescent patients, paired t-tests will not be conducted on the Haemo-QoL-SF scales. For EQ-5D-5L and Haem-A-QoL, the number of patients who reported a clinically meaningful change from baseline to Week 24 will be reported. For EQ-VAS, a meaningful change is 7 points and for the index scale it is 0.07 points (Walters et al. 2005; Pickard et al. 2007). For Haem-A-QoL a meaningful change is 7 points for the total score and 10 points for the physical health score (Wyrwich et al. 2015).

The number of days away from school/work and days hospitalized will be presented by treatment arm using descriptive statistics and 95% CIs.

[REDACTED]

[REDACTED]

Regarding the preference survey that is given to patients in Arms A, B, and D at Week 17, the proportion of patients preferring the older hemophilia IV treatment prior to enrollment in the study, emicizumab, and without treatment preference will be computed along with 95% CIs. For patients who have a preference to emicizumab, the factors influencing the preference will be treated like ordered categorical variables (e.g., from “had no influence in my treatment preference” to “was the most important factor in my treatment preference”) and will be summarized accordingly. The same approach will be applied for patients who have a preference to the old hemophilia treatment. Bar charts by preference factors may be produced to characterize the preference profile of each treatment (“emicizumab” or “old hemophilia treatment”).

[REDACTED]

[REDACTED]

[REDACTED]

[REDACTED]

[REDACTED]

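### The alpha-controlled Haem-A-QoL tests use a treatment-by-baseline interaction with no stated comparison score and omit the randomisation stratum; a main-effects ANCOVA with the stratum is a small, free improvement

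*SAP*

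**What the plan says.** SAP 4.5.2 lists "A versus C randomized comparison: Haem-A-QoL physical health at 24 weeks" and the matching B vs C comparison as the last two entries in the testing hierarchy. SAP 4.5.2.5 describes the analysis as an ANOVA: "The model will include the treatment group together with the baseline score and treatment by baseline interaction as covariates". It continues: "As for the primary analysis, a global approach with a 3-level categorical effect for treatment", to be used for A vs C and B vs C. It gives no baseline value, centring, adjusted-mean rule or contrast coefficients. I found none in SAP 2.3.2.6, 4.5.2.6 or 4.9, or in Protocol 6.5.2.

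The stratum is treated differently in the two models. Randomisation is "stratified by the number of bleeds in the last 24 weeks" (SAP 3.1). The primary negative binomial model includes the <9/≥9 bleed count "in the last 24 weeks prior to study entry as a stratification factor", taken from the eCRF (SAP 4.5.1). The Haem-A-QoL model does not include it.

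Protocol 6.5.2 names ANCOVA for the HRQoL scales and mentions no interaction. Its sentence is framed as a comparison with baseline within each arm, so it does not fully define the between-arm model.

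SAP 4.5.2.6 extends the same model to the Haem-A-QoL total score, the EQ-5D-5L index and the VAS, which "will be analyzed using the same analysis methodology as the Haem-A-QoL physical health subscore". Those three are outside the hierarchy.

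**The concern.** In a main-effects model the arm difference is one number. With a treatment-by-baseline term it is a line: the A minus C difference at baseline b equals the difference at the mean plus the slope difference times (b − mean). For example, a slope difference of 0.2 per point moves the effect by 0.2 × 20 = 4 points over 20 baseline points. A confirmatory test should say where on that line it is read.

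The stratum is a separate and smaller matter. Leaving a stratification factor out of the model keeps the test valid. It leaves between-stratum variation in the residual, and it is inconsistent with the primary analysis of the same randomised patients.

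At stake are precision and a clear definition for two secondary tests. No later test depends on them.

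**Working it through.** **Inputs from the documents.** Planned arms are 34/34/17, or 30/30/15 in the power statement (SAP 2.4). These are upper bounds, because only adults complete the Haem-A-QoL. The plan gives no power figure for these tests, so there is nothing of its own to reproduce.

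**Assumed inputs.** Residual SD 18, baseline mean/SD ratio r from 1.0 to 2.1, and a constant between-arm benefit of 10 or 15 points. SAP 4.5.3 says "For Haem-A-QoL a meaningful change is 7 points for the total score and 10 points for the physical health score". That is a threshold for an individual patient's change; using 10 points as a between-arm difference is my assumption.

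**Standard error at baseline b, A vs C.** SE(b) = s·√[1/nA + 1/nC + (b − mean)²·(1/SxxA + 1/SxxC)], with Sxx ≈ (n − 1)·SD².

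- At the mean: 18 × √(1/34 + 1/17) = 18 × 0.297 = 5.35.
- At score 0, relative to the mean: √[1 + r²·(1/33 + 1/16)/(1/34 + 1/17)] = √(1 + 1.052·r²). This ratio does not depend on the residual SD or the effect.

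| r | SE ratio, score 0 vs mean |
|---|---|
| 1.0 | 1.43 |
| 1.25 | 1.63 |
| 1.6 | 1.92 |
| 2.1 | 2.37 |

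**Power, A vs C, 34/34/17.** Simulated with ordinary least squares, two-sided 0.05, baseline normal and clipped to an assumed 0–100 range:

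| Baseline mean/SD before clipping (observed r) | ANCOVA, 10 / 15 points | Interaction at mean, 10 / 15 | Interaction at score 0, 10 / 15 |
|---|---|---|---|
| 15/25 (1.0) | 45% / 78% | 44% / 77% | 25% / 48% |
| 25/25 (1.26) | 45% / 78% | 44% / 77% | 20% / 39% |
| 40/25 (1.73) | 45% / 78% | 44% / 77% | 14% / 27% |
| 50/25 (2.1) | 45% / 78% | 44% / 77% | 12% / 21% |

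Settings of 20/20 and 30/30 add nothing: after clipping they are the 25/25 setting rescaled, with SE at score 0 of 8.85, 8.86 and 8.88. Rejection under the null is 4.7–5.6% in every version.

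The normal approximation agrees. At the mean, Φ(10/5.35 − 1.96) = 46%. At score 0 with r = 1.0, SE = 5.35 × 1.43 = 7.65 and Φ(10/7.65 − 1.96) = 26%.

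**Stratum.** Suppose the two strata are equal in size and differ by g points after baseline adjustment (g assumed). Omitting the stratum inflates the estimated SE by √[1 + (g/2)²/18²].

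- g = 0: factor 1, no loss.
- g = 5: √(1 + 6.25/324) = 1.010. Power is Φ(1.87 − 1.96 × 1.010) = 46% (45.7%), against 46.4% with the stratum: under 1 point lost.
- g = 10: √(1 + 25/324) = 1.038. Power is Φ(1.87 − 1.96 × 1.038) = 43.5%: about 3 points lost.

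Simulation with balanced strata gives 45% against 45% for g = 5, and 42% against 45% for g = 10. If the odd-sized control arm always has one patient fewer in the higher-scoring stratum (8 of 17 against 17 of 34), an imbalance of about 0.03 × g also stays in the unadjusted estimate. The loss is then about 2 points (43% against 45%) for g = 5 and about 5 points (40% against 45%) for g = 10. These are the upper values to quote.

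**The case against.** The strongest reply is that nothing is wrong in practice. Adjusted means at the overall mean baseline are the usual way to read such a model, and they cost about 1 point of power. The tests come last, hold their level and leave the bleed endpoints alone. The stratum is optional for validity. All of this stands, and it is why the point is minor.

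A reader might go further and infer that the tests will be run at score 0, the healthy end of the scale, with power cut by half or more. The inference would be that the cross-reference to the primary analysis imports its contrast. The documents do not support this:

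- In SAP 4.5.2.5 the cross-reference qualifies the single model with a three-level treatment effect. That distinguishes it from the separate A/C and B/C models listed as a sensitivity analysis for the primary endpoint in SAP 4.5.4.
- The contrast wording, "an appropriate contrast statement will allow both tests to be performed via the following hypothesis", is in SAP 4.5.1 only and belongs to a model with no interaction. A contrast that ignored the interaction terms would not be an appropriate one here.
- The size of the loss rests wholly on assumed baseline values. At r = 1.0 and 15 points, power at score 0 is 48% against 78%, a fall of less than half.

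A reader might also infer inflated type I error from the choice of readings. Each reading alone holds about 5%. Inflation would require choosing between them after seeing the data, and the documents give no sign of that.

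Two things survive. The comparison score is unwritten, and even the overall mean needs a population: SAP 4.5 bases efficacy on All Patients, which includes Arm D, while this model has only the three randomised arms. And the stratum is omitted without a reason.

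**Conclusion.** The point holds as a minor one. SAP 4.5.2.5 makes the two Haem-A-QoL comparisons depend on the baseline score without saying where they are read, and it drops the stratification factor that the primary model keeps. On the natural reading the interaction costs about 1 point of power. The omitted stratum costs nothing if the strata do not differ after baseline adjustment, up to about 2 points for a 5-point gap, and about 3 to 5 points for a 10-point gap. Only the literal score-0 contrast would be costly, with an SE 1.4 to 2.4 times as large, and the text does not call for it.

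The missing comparison score and the omitted stratum are plain from the text. Every power figure depends on assumed means, SDs, effects and stratum gaps.

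**What to change.** In SAP 4.5.2.5, and by reference in 4.5.2.6, specify:

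- The Week-24 score is analysed with treatment (three levels), baseline score and prior-bleed stratum (<9/≥9, from the same source as the primary model).
- A vs C and B vs C are tested as adjusted mean differences.
- Treatment-by-baseline moves to a sensitivity analysis. If it stays in the main model, the arms are compared at the mean baseline score of the analysed randomised patients.

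Either option fixes the tested effect with almost equal power, and the first matches the method that Protocol 6.5.2 names. The cost is one to three lines of SAP text before the analysis and one degree of freedom for the stratum. No new data are needed, since baseline score and prior bleeds are already collected. If the interaction is moved, unequal slopes are examined only in the sensitivity analysis.
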